### ***Participants and procedures***

Participants were adult women clinically diagnosed with SUD and admitted to the residential SUD treatment program study site. Upon admission, all patients met one-on-one with the site's intake clinician coordinator who conducted an assessment for substance use disorders, mental health disorders, and suicidality using the DSM-5. At that time, the same clinician also completed a psycho- social assessment using an in-house form to identify important aspects of patient history and patient needs to inform case management and treatment plan. The site psychiatrist and on-site clinician coordinator discussed diagnostic assessment, determined final diagnoses, and made record in the patient chart. The site intake counselor verified study eligibility, and for those women who were eligible, informed clients about our study. The names of clients who assented to be contacted by the study team were provided to the study interviewer. The study interviewer made appointments with prospective participants, conducted the informed consent and HIPAA process, and administered the baseline assessment interview. As part of the site's normal post-admission protocol, patients began receiving services as usual including individual and group therapy, psychoeducation groups and other services. Psychoeducation and therapy groups were scheduled on a six-week cycle.

Inclusion criteria for the research trial were: client at the residential treatment study site, female, adult aged 18 to 65 years, diagnosed with SUD via clinical record, fluent in English, and agreed to participate in the study. Exclusion criteria were: inability to comprehend or sign informed consent, cognitive impairment, untreated psychotic disorder or severe chronic mental health condition based on clinical intake LR- DSM-IV or DSM-V diagnostic assessment, older than 65 years of age as this was unusual at the site, reported suicidality during the prior 30 days based on clinical intake assessment, current prisoner, more than 6 months pregnant, and not willing to sign a HIPAA form or be audio recorded during interviews and intervention sessions. Study interventions were held separately two times per week during the same time slot. Study participants joined the first session of their assigned group, which started every six weeks per study site protocol.

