To minimize bias across study groups related to participant characteristics and histories, we applied urn randomization as implemented by the Urn Randomization Program (version 1.01) after a group of 10 to 30 women were deemed eligible for randomization. Strata variables were current pregnancy (yes or no) and age (18 to 31 years or 32 to 65 years) to ensure these characteristics were equivalent across groups at baseline because they can affect SUD treatment outcomes. The urn approach is robust against experimental bias in clinical trials because it is a compromise between perfect balance in treatment assignments and complete randomization to eliminate experimental bias.

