### ***Neurobiology of addiction (NA) psychoeducation attention control***

This intervention was delivered twice weekly for 80 min each for a total of 12 group sessions (6 weeks) during residential treatment. NA was guided by an instructional manual with standardized lesson plans (Amaro et al., 2016; unpublished facilitator's manual). The curriculum was previously developed by [name] over 3 years with input and review from focus groups of women and providers in SUD treatment, and subsequently reviewed by three experts in NA. A masters-level educator with a background and training in the NA facilitated all sessions and an on-site masters-level clinician with experience in SUDs and training in NA co-facilitated the intervention. Participants received didactic education on the structure and function of the brain and the neurobiology of addiction. Although educational and centered on knowledge acquisition, the program has no proven efficacy in altering substance use behavior. It included didactic psychoeducational presentation using PowerPoint, video recordings, exercises, games, and group discussions to reinforce the session content and respond to questions. Sessions did not address behavior change strategies, stress reduction, mindfulness, or relapse-related content. Films, videos, exercises, activities, and discussions were used to explain content and promote participant engagement. Topics included: (1) definition of addiction and why it is a brain disease; (2) brain structures and functions and those related to addiction; (3) effects of various types of substances on the brain; (4) rewarding effects of substances and how these effects lead to addiction; (5) definitions and brain functions related to craving and withdrawal; and (6) the roles of treatment in recovery. Participants were expected to gain knowledge pertaining to

basic brain structure and function and the effects of drugs on both. The intervention was equivalent to MMWR in time, teacher attention, expectancy of benefit, and group support. Participants received a NA Participant Workbook organized by session that included session specific information covered in each session such as selected PowerPoint slides and were asked to bring these to class to help them identify questions they had from the previous session. Participants received MP3 players with audio clips of key sections of videos introduced in class.

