ending 150 days later. Participants with the discharge status of completer, non-completer with significant progress, and in-residence were coded as 1 for “retention”. Participants with the discharge status of non-completers without significant progress were coded as 0 for “non-retention”. Our examination of the survival curves revealed that group curves crossed at 50 days from the start of the intervention, which indicated the need for a piecewise model. Thus, a multivariable, 2-piece model (i.e., Piece 1 predicting outcome events during day 0 to 50 and Piece 2 predicting outcome events for days 51 to 150) was calculated. The first piece of the model coincided with the study intervention period and the second piece to the post-intervention period. Adjusted Cox proportional hazards regression (PROC PHREG), with days as the time scale, provide estimates of hazard ratios (HR) and the 95% confidence intervals (CI) for the non-retention outcome event. HR effect size estimates are categorized as small (0.77), medium (0.53), and large (0.36) (Amaro et al., 2016). We conducted logistic regression (PROC LOGISTIC) to test for group differences in satisfactory progress among the subgroup of non-completers. We used general linear mixed models (PROC MIXED) to examine differential changes in the self-reported mechanism of action variables from pre-intervention to post-intervention by group, adjusting for covariates. We used Pearson r to test for correlation between class attendance (as a dosage variable) and change in mechanisms of action measure scores. Pearson r effect sizes are small (.10), moderate (0.30), or large (0.50). All analyses were conducted in SAS version 9.4 (SAS Institute). All models used a maximum likelihood estimated approach to account for missingness.

Substance Use and Relapse

To quantify substance use at the three assessment points (baseline, postintervention, and follow-up), our trained study staff used the TLFB measure, which is a comprehensive retrospective calendar-based validated semistructured interview measure of daily substance use (29). From TLFB data, we calculated substance use from study intervention start date

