80% power, and a 35% probability of substance use in the control group. Our ITT analysis of $N = 200$ did not include the 25 women randomized to a study group who never showed up to the first class and were thus excluded from analysis based on receiving no dose of the intervention. Prediction models included clinical covariates identified a priori as having conceptual relevance for their impact on the effect of study intervention on recovery (i.e., number of mental health diagnoses coded as SUD only, one co-morbid mental health diagnosis, two or more comorbid mental health diagnoses, adult- hood trauma exposure [summed domain score from Life Stressor Checklist Revised], PTSD diagnosis via the Diagnostic and Statistical Manual of Mental Disorders [5th Edition], and PTSD symptom score [PTSD symptom Scale Self Report]). These models also adjust for an inherent study design variable (i.e., days in residential treatment before study intervention start date). Unadjusted models as effect size confirmation is located in the online supplement. We use the piecewise Cox regression PHREG procedure in SAS version 9.4 (SAS Institute) to model time periods during and after the study intervention (i.e., piece 1 predicting outcome events during the intervention period and piece 2 predicting outcome events after the intervention). Resulting HR effect sizes are interpreted as small (0.77), medium (0.53), and large (0.36) (35). Next, because of the zero-inflated distribution of days of substance use, we use negative binomial hurdle models to estimate any use (versus abstinence) and days of use among users simultaneously (36). Finally, we compute unadjusted and adjusted proportional estimates for group differences in relapse status (i.e., abstinent, lapse, relapse), and effect size is expressed as odds ratios (ORs).

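### The substance-use analysis labelled ITT (N = 200) leaves out 25 randomised women who missed the first class; it is a modified ITT set, and no all-randomised analysis of substance use is described.

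*SAP*

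**What the plan says.** In the Data Analysis section for substance use, the SAP gives an analytic sample of 200 and calls the analysis ITT. The same sentence says that it "did not include the 25 women randomized to a study group who never showed up to the first class and were thus excluded". The ground given is that these women had none of the assigned classes. The only additional models mentioned there are unadjusted ones: "Unadjusted models as effect size confirmation is located in the online supplement".

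The order of events is in the Protocol, Participants and procedures. Urn randomisation took place "after a group of 10 to 30 women were deemed eligible for randomization". Then, "Study participants joined the first session of their assigned group, which started every six weeks per study site protocol". First-class attendance therefore follows assignment.

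On missing data, the SAP's first Data analysis section (retention and mechanism measures) says: "All models used a maximum likelihood estimated approach to account for missingness". That section also names an ITT approach for retention, but gives no N and no rule for women who did not attend.

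**The concern.** Intention-to-treat means analysing women in the arm to which they were randomised, whatever dose they received. A set defined by attending the first class is selected after randomisation, so the ITT label claims a protection that this set does not automatically have.

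If assignment affected which women attended, the attenders in the two arms would no longer be comparable, and the substance-use estimates could shift toward benefit or toward harm. The documents do not give the split of the 25 by arm, their reasons, or whether women knew their assignment before the first class. A reader therefore cannot judge how far the label misleads.

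**Working it through.** **Inputs.** From the SAP, substance-use Data Analysis: N = 200 analysed, 25 excluded, HR 0.51, two-sided 5%, 80% power, 35% use in the control group. Assumed, because not stated: 225 randomised in total, and 112.5 per arm. Splits of the 25 are written MMWR/NA.

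**The plan's own figure.** Schoenfeld events = 4 × (1.960 + 0.842)² / (ln 0.51)² = 69.2, rounded up to 70; 70 / 0.35 = 200. This reproduces N = 200 when 35% is used as the overall event rate. So 200 is the powered analysis set, not the number randomised.

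**Share left out.** 200 + 25 = 225; 25 / 225 = 11.1%. Any further exclusions would raise this share.

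**Does anything bring the 25 back?** Covariate adjustment acts on the women analysed. The supplement is described as unadjusted models. Maximum likelihood is not said to cover women removed from the set. For substance use, the answer from these documents is no.

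**Case A: no-show does not depend on arm.** An uneven split is then chance, and attenders in the two arms stay exchangeable. This was simulated with 225 women, 25 no-shows unrelated to arm, all 25 of them users, a log-rank test on the 200, and 60,000 runs. False-positive rates by number of no-shows in MMWR were 5.4% (10 or fewer), 4.9% (11 to 14), 4.7% (15 to 16) and 4.5% (17 or more), with mean z about 0 throughout. There is no bias at any split.

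**Case B: assignment affects who attends.** Suppose there is no true effect and use is 35% in each arm as randomised. With k no-shows in an arm, each at an assumed risk q of 60% to 100%:

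- attender risk = (0.35 × 112.5 − q × k) / (112.5 − k)
- HR = ln(1 − p_MMWR) / ln(1 − p_NA)
- z = ln(HR) × √(events × f × (1 − f)), where f is the MMWR share of attenders and events are 63.75 (q = 0.6) or 53.75 (q = 1.0)
- false-positive chance = Φ(−1.96 − z) + 1 − Φ(1.96 − z)

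| Split | HR, q = 0.6 to 1.0 | False-positive chance |
|---|---|---|
| 8/17 | 1.10 to 1.34 | 6.7% to 18.7% |
| 10/15 | 1.06 to 1.17 | 5.5% to 9.0% |
| 13/12 | 0.99 to 0.97 | 5.0% to 5.2% |
| 15/10 | 0.95 to 0.85 | 5.5% to 9.0% |
| 17/8 | 0.91 to 0.75 | 6.7% to 18.7% |

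Example, 15/10 with q = 1.0: (39.375 − 15) / 97.5 = 25.0% against (39.375 − 10) / 102.5 = 28.7%, so HR = 0.85. If no-shows also have 35% risk, HR is 1.00 at every split. These are whole-period figures. They show the mechanism, not the bias in the planned piecewise, hurdle or relapse-status estimates.

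**What an all-randomised analysis could show if the 200 give HR 0.51.** MMWR attender risk = 1 − 0.65^0.51 = 19.7%; NA attender risk = 35%. Arm risk = (attender risk × attenders + assumed users among the no-shows) / 112.5.

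| Split | 25 at 35% risk | None use | All use | Only NA no-shows use | Only MMWR no-shows use |
|---|---|---|---|---|---|
| 10/15 | 0.55 | 0.55 | 0.55 | 0.35 | 0.87 |
| 13/12 | 0.56 | 0.51 | 0.63 | 0.35 | 0.91 |
| 15/10 | 0.57 | 0.49 | 0.69 | 0.36 | 0.94 |

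At 35% risk, 8/17 gives 0.54 and 17/8 gives 0.58. Example, 13/12 at 35%: (99.5 × 0.1972 + 13 × 0.35) / 112.5 = 21.5% against 35.0%, so HR = 0.56. Imputing each no-show from her own arm's attenders returns 0.51 at every split, so it tests nothing.

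**The case against.** The strongest reply is that the SAP hides nothing: the number excluded and the reason stand beside the label. The Protocol also gives grounds to think that attendance did not depend on arm. On timing: "Study interventions were held separately two times per week during the same time slot". On the control condition: "The intervention was equivalent to MMWR in time, teacher attention, expectancy of benefit, and group support". If women did not know their assignment before the first class, it could hardly have affected whether they came, and the comparison would be unbiased for attenders. The split, reasons and baseline data are also results items that may appear in a report not available here.

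Most of this stands, and it limits the point. A reader might infer that the published comparison is biased, or that an uneven split would prove it. The documents support neither reading: Case A shows no bias at any split, and the Case B figures apply only if assignment affected attendance. The highest rate, 18.7%, also needs a 17/8 or 8/17 split and use by every no-show, and the documents support neither assumption. A move from 0.51 to 0.56 would likewise reflect counting untreated women as untreated.

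A reader might also extend the point to retention. The documents do not support that. Retention is called ITT with no N and no exclusion stated, so its set may or may not hold all randomised women.

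None of this rescues the label. Disclosure allows a careful reader to spot the exclusion, but a set chosen by attendance after randomisation is still not ITT.

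**Conclusion.** The label is wrong as written. The substance-use set is modified ITT and omits 25 of an inferred 225 randomised women (11.1%); no all-randomised analysis of substance use is described. This conclusion rests on the SAP's own sentence and on the Protocol's order of randomisation and first class.

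Bias is possible, not shown. Its size and direction depend on whether assignment affected attendance and on the no-shows' risk, and the documents settle neither. The hazard ratios above also assume 1:1 arms and apply the SAP's 35% planning figure. This should be fixed, but it does not overturn the N = 200 analysis.

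**What to change.** 1. Relabel N = 200 as *modified ITT (attended first class)* and stop describing its results as ITT. It can remain the stated analysis.
2. Add an all-randomised sensitivity analysis by assigned arm for time to first use, any use and days of use, and relapse status. Start time at the assigned group's scheduled first class, which matches the start date used for attenders. Use any timeline follow-back (TLFB) data held on the 25. Where these are missing, use control-based imputation and bounds: all users, none, and opposite assumptions by arm. For relapse status, take all relapsed or all abstinent; for days of use, state the assumed count. Do not impute from the attenders' arm effect.
3. Alongside it, report the 25 by assigned arm with reasons and baseline characteristics. Baseline interviews preceded randomisation (Protocol, Study design), so baseline data should exist.

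The cost is a wording change, a short account of counts, and modest programming. The result will depend partly on missing-data assumptions. Interviews were timed from the end of the intervention, and the documents do not say whether the 25 were interviewed after baseline. The opposite-extreme bounds are wide (about 0.35 to 0.94 across the 10/15, 13/12 and 15/10 splits), and the estimate may be less favourable than 0.51.

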through the day of the last intervention session date (6 weeks later) and from intervention end date to 7 months later (8.5-month follow-up period in total). The interview window for postintervention assessment was 1 to 14 days after the intervention end, and for the follow-up assessment, the window was 7–9 months after the intervention end, and this variability was dependent on participant availability. This allowed for the quantification of daily substance use from study intervention start date to study end point. TLFB data allowed us to operationalize three substance use outcomes for any drug use and alcohol to intoxication as well as methamphetamine and cannabis/marijuana, including the following: time to first use, quantified as days until first any drug use or alcohol intoxication; days of use, quantified as the total number of days in which any drugs were used or alcohol intoxication occurred, and relapse status, quantified according to a) abstinent, did not use during the period after the study intervention; b) lapse, used after study intervention but did not revert to regular use on one-third or less of days after first use; and c) relapse, used substance after the study intervention and continued to use regularly on more than one-third of days from first use.

Alcohol and Drug Use Confirmation Tests

Breathalyzer (for alcohol) and urine (for drug) samples were collected at postintervention and follow-up. We calculated agreement rates for any and each drug (excluding alcohol) against TLFB self-report. Only two participants had a positive Breathalyzer result. For urinalysis, we compared TLFB drug use reports for 3 days before the urinalysis date against the urinalysis result.

Data Analysis

Our analytic sample size of 200 was powered to detect a medium-sized effect (Cox regression hazard ratio [HR] = 0.51) for days until first drug use with a two-sided $p < .05$ significance level,

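### Time to first use is sized on one hazard ratio but analysed only as two period-specific ratios, so the stated 80% power applies to neither, and no test compares the two

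*SAP*

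**What the plan says.** All of this is in the SAP's Substance Use and Relapse part.

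- **Sizing.** The Data Analysis section says the sample was "powered to detect a medium-sized effect (Cox regression hazard ratio [HR] = 0.51) for days until first drug use", at a "two-sided $p < .05$ significance level", with "80% power, and a 35% probability of substance use in the control group". This is one HR for one endpoint.
- **Analysis.** The same section models time to first use by piecewise Cox regression: "piece 1 predicting outcome events during the intervention period and piece 2 predicting outcome events after the intervention". Each HR is then read against size benchmarks of 0.77 (small), 0.53 (medium) and 0.36 (large).
- **Periods.** The intervention lasts six weeks. Follow-up from its start is 8.5 months in total.
- **Not described.** There is no whole-period HR, no log-rank test of first use, no treatment-by-period term, and no statement of which piece is decisive. Unadjusted models are mentioned as confirmation of effect sizes, but nothing says they drop the split. The hurdle model and the relapse categories address any use, days of use and relapse status, not time to first use.

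**The concern.** A power statement tells the reader how likely the planned analysis is to detect the stated effect. Here the planned analysis divides the events in two, so each reported HR rests on fewer events than the statement assumes. The question of whether MMWR delays first use gets no single time-to-event answer.

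The second risk is interpretive. Piece 1 covers about one sixth of the follow-up, so unless first use is concentrated early it will have the fewer events and the lower power. A non-significant piece 1 beside a significant piece 2 could then be read as a benefit that starts only when the classes end. That reading needs evidence that the two HRs differ, and no such comparison is planned.

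**Working it through.** **Inputs from the SAP:** N = 200, HR 0.51, two-sided 5%, 80% power, 35% probability of use, six weeks (42 days) of intervention, and 8.5 months (about 259 days) in total.

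**Assumptions, not in the documents:** 100 women per arm, even hazard, HR 0.51 throughout and no censoring.

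**Step 1: reproduce the plan's figure.** Schoenfeld's formula gives 4(1.96 + 0.84)² / (ln 0.51)² = 69.2, or 70 events.

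- If 35% is the overall event probability, 70 / 0.35 = 200. This matches the plan.
- If 35% is the control probability, as worded, the other arm has 1 − 0.65^0.51 = 19.7% and the mean is 27.4%. That gives 54.7 events among 200 women. Power is Φ(½√54.7 × 0.673 − 1.96) = 70%.

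Both readings are carried forward. The second column below needs a control probability of 44.2%, for which the mean of the two arms is 35%.

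**Step 2: divide the events.** Piece 1's share of the control cumulative hazard is 42/259 = 0.162. On the control reading, that hazard is −ln 0.65 = 0.431. Piece 1 events are 100(1 − e^(−0.431 × 0.162)) + 100(1 − e^(−0.431 × 0.162 × 0.51)) = 6.8 + 3.5 = 10.3. The remainder fall in piece 2.

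**Step 3: power by piece,** from Φ(½√events × 0.673 − 1.96):

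| | 35% = control | 35% = overall |
|---|---|---|
| Events, piece 1 / piece 2 (rounded separately) | 10.3 / 44.5 | 13.8 / 56.2 |
| Power, piece 1 | 19% | 24% |
| Power, piece 2 | 61% | 71% |
| Power, whole period | 70% | 80% |
| Piece 2 significant, piece 1 not | 50% | 54% |

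The last row is power₂ × (1 − power₁), for example 0.612 × 0.811 = 0.497. For the control reading, 20,000 simulated trials with a log-rank test in each piece gave 16%, 60%, 69% and 51% for the four probability rows.

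**Step 4: relax the even hazard.** With the cut at day 42, piece 1's share of the control hazard was varied from 6.5% to 40% under both readings. Piece 1 then expects 4 to 32 events, and the piece-2-only pattern occurs in 28% to 68% of trials.

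**Step 5: precision of piece 1.** With 10.3 events, a 95% interval centred on 0.51 is 0.51 × exp(±1.96 × 2/√10.3), or about 0.15 to 1.73. The estimate must fall below about 0.29 to be significant. With 10 events and no true effect, it would still be at or below 0.53, the medium benchmark, with probability Φ(ln 0.53 / (2/√10)) = 16%.

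**Step 6: can the two HRs be told apart?** The standard error of the log ratio of HRs is √(4/10.3 + 4/44.5) = 0.69, or √(4/13.8 + 4/56.2) = 0.60. A treatment-by-period test reaches 80% power only at a ratio of about exp(−2.80 × 0.69) = 0.14, or exp(−2.80 × 0.60) = 0.19.

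**The case against.** The split has a rationale: it follows a design boundary, the end of the classes. The SAP also found crossing survival curves for retention, so a constant HR is not a safe default. That evidence concerns retention, though, and the substance-use section offers none of its own for first use. Nor does the SAP state that it will compare significance across pieces. It labels effect sizes, and under a constant HR of 0.51 with 10.4 events piece 1 would itself be labelled medium or larger about 52% of the time. This stands: the misreading is a risk that the plan leaves open, not a rule that it adopts.

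The treatment-by-period test is weak, as step 6 shows. Its use is to restrain claims. A non-significant result would not show that the HRs are equal.

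A reader might infer more than the documents support:

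- **That the whole-period HR should replace the pieces as the headline.** This is a trade-off. If there is truly no effect during the classes, the whole-period HR is diluted to about 0.60 and has about 49% power, against about 60% for piece 2 alone.
- **That about 10 events is a planned or observed count.** The SAP gives no event count by period. The figure is an expectation under the assumptions listed.
- **That the piece-2-only pattern is always the likeliest under a constant HR.** With 35% control use and 40% of the hazard in piece 1, it occurs in 28% of trials, against 33% with neither piece significant.
- **That methamphetamine and cannabis models will fail for want of events.** The SAP lists these substances among its outcomes but gives no risks for them, and separate Cox models are only an inference.

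Finally, the protocol's Study design section says the trial was designed to compare retention days. First use is not named as primary, which limits the weight of the point.

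**Conclusion.** The point holds as a mismatch between sizing and analysis. The 80% power is claimed for one HR. The SAP reports two others and describes neither a whole-period HR nor a test that the two differ. That much is read directly from the text.

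The size depends on the listed assumptions. Neither piece reaches 80% on either reading of the 35%: piece 1 has about 19% to 24% power and piece 2 about 61% to 71% with even hazard. Significance in piece 2 alone is expected in about half of trials with an unchanged HR, so it cannot by itself support a claim that the benefit arises only after the classes.

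The documents do not show that the split is wrong or that such a claim will be made. This is a gap in reporting and interpretation that should be closed. It does not invalidate the piecewise model.

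**What to change.** 1. Report the whole-period HR for time to first use, the quantity the trial was sized on, alongside the two pieces.
2. Report the treatment-by-period test with the pieces and note its low power. Do not infer a during/after difference from one piece being significant and the other not.
3. State that the 80% power applies to neither piece. Give the expected or observed events and the confidence interval for each piece next to any small, medium or large label.
4. Label the whole-period HR and the treatment-by-period test as added after data collection. The SAP already reports breath-test results, so it was written after data were collected, and the additions should not look pre-specified.

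Firth estimation is optional if a piece has no events in one arm.

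The cost is a few sentences in the SAP, one model with a single arm term and one interaction term. No new data are needed and both pieces are kept. While editing the power statement, say whether 35% is the control or the overall probability, since only the overall reading gives 200.

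### The adjusted substance-use models have no small-sample inference: the days-of-use test can be too liberal if a substance has about 40 users or fewer, and the piece 1 hazard ratio is infinite if an arm has no event

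*SAP*

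**What the plan says.** The SAP section Substance Use and Relapse defines time to first use, days of use and relapse status "for any drug use and alcohol to intoxication as well as methamphetamine and cannabis/marijuana". Under the Data Analysis heading that follows, one adjustment set serves all of these: "Prediction models included clinical covariates identified a priori as having conceptual relevance". The set has five items and six model terms:

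- number of mental health diagnoses, three levels (2 terms)
- adulthood trauma score (1)
- PTSD diagnosis (1)
- PTSD symptom score (1)
- days in residence before the intervention began (1)

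Days of use are analysed with a hurdle model: "we use negative binomial hurdle models to estimate any use (versus abstinence) and days of use among users simultaneously". Time to first use is analysed with a piecewise Cox model in PROC PHREG, with one piece during the intervention and one after it. The SAP does not say whether covariate effects are common to both pieces.

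The sample size statement reads "Our analytic sample size of 200 was powered to detect a medium-sized effect", with "Cox regression hazard ratio [HR] = 0.51) for days until first drug use" and "80% power, and a 35% probability of substance use in the control group". The 200 already leaves out "the 25 women randomized to a study group who never showed up to the first class".

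Unadjusted models are placed in an online supplement to confirm effect sizes, and relapse status is reported both ways. No penalised, exact or permutation method is named, and no number of users is given for either named substance.

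**The concern.** The count part of a hurdle model is fitted to users only, so its sample size is the number of users, not 200. With an intercept, group, six covariate terms and a dispersion parameter it has 9 parameters. Standard errors from maximum likelihood rest on large-sample theory. With few users per parameter they tend to be too small, so p-values are too small and intervals too narrow. The error runs towards declaring an effect, and it would fall on the substance-specific results, where users are fewest.

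Piece 1 of the Cox model covers six weeks of an 8.5-month follow-up and so holds few events. If one arm has none, the ordinary partial-likelihood estimate of the piece 1 hazard ratio is zero or infinite, and its Wald interval means nothing.

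**Working it through.** **Inputs from the SAP.** N = 200; HR 0.51; two-sided 5%; 80% power; 35% use; piece 1 of 6 weeks; follow-up of 8.5 months. **Assumptions.** 1:1 allocation (the ratio is not stated), constant hazard, 42 of 255 days in piece 1, and a Wald test (the SAP names no test).

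**1. The plan's own figure.** Schoenfeld events = 4 × (1.960 + 0.842)² / (ln 0.51)² = 31.4 / 0.453 = 69.2, so 70. Then 70 / 0.35 = 200. The stated N is reproduced if 35% is the overall probability of use. The text assigns it to the control group, so both readings are carried forward.

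**2. Users of any substance.**
- 35% in control: the other arm has 1 − 0.65^0.51 = 19.7%. Users = 200 × (0.350 + 0.197)/2 = 54.7.
- 35% overall: 200 × 0.35 = 70.

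Per parameter in the count part: 55/9 = 6.1 or 70/9 = 7.8. An assumed 20 to 30 users of one substance would give 2.2 to 3.3.

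**3. Error rate of the group Wald test in the count part.** Zero-truncated negative binomial fits were simulated under no group effect. Days of use were drawn from several assumed distributions: negative binomial with mean 30 or 40 and dispersion 0.5 to 1.0, one version capped at 255 days, and a beta-binomial bounded at 256 days. Each cell had 400 to 1,000 runs. Monte Carlo error at a 12% rate is about 1.3 points with 600 runs: √(0.12 × 0.88/600).

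| Users | Group + six terms | Group only |
|---|---|---|
| 20 | 13-16% | 3-9% |
| 30 | 7-12% | 3-8% |
| 40 | 8-11% | 6-7% |
| 55 | 4-9% | about 6% |
| 70 | 6% | 4-6% |

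A t reference does not cure it: 11-13% at 20 users and 7-10% at 40. With 15 users the adjusted Wald rate was 18-22%.

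**4. Events in piece 1.**
- 35% in control: 1 − 0.65^(42/255) = 6.8% in control and 1 − 0.65^(0.51 × 42/255) = 3.6% in the other arm. Events = 100 × (0.068 + 0.036) = 10.4.
- 35% overall: 200 × 0.068 = 13.7.
- A substance accounting for half of the events would have about 5 to 7.

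**5. Chance that an arm has no piece 1 event.** With no effect and m events it is 2 × 0.5^m: 6.3% at 5 events and 0.2% at 10. At HR 0.51 with 100 women per arm:
- about 10 events expected: 0.65^(0.51 × 42/255 × 100) = 2.7% for the MMWR arm, plus 0.1% for control, about 3%;
- half that hazard: 16.4% + 2.9% − 0.5% = about 19%.

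**6. Do the covariates break the Cox fit?** In a joint fit with shared covariate effects under no group effect, non-finite estimates arose in 4-6% of runs at 5 piece 1 events and in under 1% at 8 or more. That matches the zero-event arithmetic, so the covariates add essentially nothing. If piece 1 is fitted alone with all seven terms, some coefficient was non-finite in 45% of runs at 5 events, 5% at exactly 10 and 2% at 12. With HR 0.51 and a count varying around 10, it was 16-19%. Finite piece 1 fits were not too liberal (0-5%).

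**The case against.** The strongest reply is that the documents give no number of methamphetamine or cannabis users. At the only counts they imply, 55 to 70 users of any substance, the excess is small. That stands. A reader might infer that the substance-specific results will carry too many false positives. The documents support only the conditional statement, because either substance could have more than 40 users.

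Second, the covariates are not the whole cause. Some excess remains with group only in the negative binomial simulations, so part of it belongs to the Wald test in small samples. That also stands, and it argues for changing the inference rather than the covariates.

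Third, the unadjusted models already give a reader something to compare with. They do, but the SAP assigns them to effect-size confirmation in a supplement and does not say which result governs if the two disagree.

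Fourth, a reader might infer that six covariates will make the piece 1 Cox model fail. That needs piece 1 to be fitted alone with few events. The SAP does not say so, and its retention section describes the parallel analysis as a single two-piece model. An infinite covariate coefficient also need not make the group hazard ratio infinite. What remains is the arm with no event, which can occur with or without covariates.

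Finally, a reader might want to cut the covariates by a users-per-parameter rule, or keep only one PTSD term. The documents do not support either. This section calls the set prespecified, a cut based on observed counts would make it depend on the data, and the SAP does not say which diagnoses enter the diagnosis count. The retention section gives a different origin for the same set, but that is a separate matter.

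**Conclusion.** The concern holds in conditional form. If a substance has about 40 users or fewer, the adjusted group test in the days-of-use count part can reject at about 8-11% (40 users), 7-12% (30) or 13-16% (20) instead of 5%. The any-use count model is only mildly affected, at about 4-9%. These rates rest on assumed day-count distributions and covariate patterns, and on Wald inference. The user counts for single substances are a range, not a figure from the plan.

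For the Cox model the supported point is narrower. At about 5 to 10 piece 1 events, an infinite hazard ratio from an arm with no event is possible: about 3% to 19% at HR 0.51, and 0.2% to 6% with no effect. This assumes a constant hazard, and the risk rises if use is rarer while women live in the residence. The documents do not support saying that the covariate set as such makes the Cox model fail.

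**What to change.** In the Data Analysis section on substance use:

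1. Keep the covariate set as listed. For the count part, take the p-value for group from a permutation (re-randomisation) test that respects the urn strata of pregnancy and age, at least for methamphetamine and cannabis. Report the number of users by arm, and the unadjusted count model beside the adjusted one.
2. State that time to first use is fitted as one PROC PHREG model, with a group effect for each piece and covariate effects shared across both pieces.
3. Use the FIRTH option with profile-likelihood limits for the piece 1 hazard ratio, and report piece 1 events by arm.

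The cost is SAP wording, a little more programming, and slightly wider intervals or larger p-values. No new data are needed. One limit remains: if the intervention changes who uses at all, users are a selected group, and neither the Wald nor the permutation test removes that.
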